9.4 Statistical Analyses

9.4.1 General Approach

Data Management. Data will be gathered using Penn's REDcap data collection system, a direct-entry data system where subjects can directly enter responses. REDcap is HIPAA compliant and data is secured on Penn Medicine's data management unit (DMU) network. Interview data and self-report data are entered directly into REDcap at the research sites, by research technicians and study subjects respectively. Field validation (eg, no out of range or otherwise invalid responses will be accepted) and form validation (e.g. logically impossible responses to different questions will not be accepted) are built into this entry process. Data are transmitted (128-bit encrypted form) over the internet to the DMU servers. After online reviews, the data are archived on the servers. Certain DMU staff members have permission to modify the archived data. Audit logs record any modification to the original entry. Password protection allows members of the research team appropriate levels of data access. At time of data collection clinical research staff will review data collected for completeness (field and form validation). Weekly routine data inspections will be performed by clinical research staff to ensure data integrity. Subject brain scan data are extracted via CAMRIS web-servers and are archived to lab-specific, encrypted servers for standard cleaning and analysis.

Data Analyses. [name], the CSA Statistician, and his staff will perform the data analyses. Prior to analyses, standard data screening/cleaning procedures will be applied ⁵³. These procedures will screen the data for data-entry errors, check for outliers, assess the extent and pattern of missing data, and check that appropriate assumptions of normality are met whenever necessary. Due to sample size, it is unlikely that the randomization will result in significant imbalance of the distributions of demographic or other variables across treatment groups. Additional covariates will be considered for inclusion in the analyses, to improve the precision of estimation for the treatment effects. Covariates describing levels of cocaine use prior to the study may be included. Assumptions underlying the application of statistical methods will be examined, through use of standardized residuals, influence diagnostics, and graphical displays.

Primary Hypothesis: Estimate the differential brain fMRI response between XRNTX and XRBUP in OUD treatment groups. We hypothesize that **(H1)** XRBUP and XRNTX will modulate

the regional brain activity in the two-key cognitive-behavioral domains and measures of brain connectivity from pre-treatment (PRE) to on-treatment (ON) and this response will differ between the two medications. Milestone for transition to Phase 2: The MAT group (XRNTX, XRBUP) by Session (PRE, ON) **interaction** will have at least small ($d' \geq 0.2$) effect size in all brain measures.

H1a: Incentive salience (opioid cue-reactivity task): The decrease in the brain response to drug related stimuli (ON minus PRE) in the medial prefrontal cortex (mPFC) and the ventral striatum (VS) will be **greater** in the XRNTX than in the XRBUP group.

H1b: Executive function (Go-NoGo task): XRNTX will improve the efficiency of response inhibition more than XRBUP, leading to a greater **decrease** in the brain signal (ON vs PRE) during the NoGo trials in the inferior frontal cortex in the XRNTX group.

H1c: Resting state functional connectivity (rsFC): change (ON vs PRE) in the rsFC between the VS and the right inferior frontal gyrus (rlIFG) and the mPFC will be **greater** in the XRNTX (vs. XRBUP group).

Secondary Hypotheses: Confirm in the full sample (n=140), the significance of MAT (XRNTX, BUP-NTX) by Session (PRE, ON) interaction in all domains from Aim 1. Test the explanatory value of integrated brain-behavior models of relapse vulnerability, identify differences in variable loading between MAT group, and explore potential mechanism of individual variability in treatment outcome.

H2a: Using logistic regression, we will test the explanatory value of brain signal in modeling treatment failure and identify specific variables that differentiate MAT groups (interaction).

H2b (Exploratory): Test if the models that include brain response better explain treatment success or failure when compared to those fitted solely with demographic and clinical measures: demographic + clinical measures vs. demographic + clinical measures + brain response).

Missing Data and Nonadherence: For the longitudinal analyses described above, premature discontinuation from treatment and occasional missing daily use indicators will lead to incomplete data. The mixed effects models described above can make use of all available data provided by subjects, but the inferences drawn from them will be unaffected by the missing data only if the missing data can be regarded as ignorable, in the sense of Laird ⁵⁵. To assess the sensitivity of our analyses to this assumption, we will use shared parameter models, which allow for correlated random effects underlying the cocaine use measurements and the pattern of dropout ⁵⁶. We will also use selection models to examine the effects of missing data ^{57,58}. We will explicitly model the probability of premature discontinuation at a time point as a function of baseline characteristics and responses at previous time points, using a logistic regression model, and incorporate the predicted probabilities into a weighted analysis of the main hypotheses. We will do analyses in a range of assumptions and assess the sensitivity of results to them ⁵⁸. We will use urine drug screens, record of clinic visits and receipt of injectable medications as measures of compliance with assigned medication regime. We will use the methods of Nagelkerke et al ⁵⁹ and Small et al ⁶⁰, to obtain estimates of the intervention effect in a population compliant with treatment i.e. the Complier Average Causal Effect (CACE).

Safety: The adverse event responses will be analyzed as a measure of safety. Total number of adverse events, adverse events leading to discontinuation (in the judgment of the study physician), % of patients reporting at least one adverse event, clinical lab assessments, vital signs and

evidence of clinical worsening (by urine drug screen results and TLFB results) will be considered in assessment of safety. In a manner parallel to the analysis for therapeutic response, medication group, gender, age and other clinical variables will be entered into a generalized linear mixed effects model to predict adverse events.

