3.1 General Design

Study Design: The proposed study is a prospective open label 2-group study to compare the brain and behavioral responses of individuals with OUD receiving XRBUP and XRNTX treatments. The study will be conducted in two phases – Phase 1 = feasibility and Phase 2 = confirmation. Study interventions (XRNTX and XRBUP) and their duration will be same in both phases. Phase 1 (2 years) will have more cognitive and behavioral probes, some of which may not survive into Phase 2 (3 years) if found to not yield significant discrimination between the study interventions (groups). Participants will be men and women with current DSM-5 diagnoses of opioid use disorder (OUD) who will be randomized to XRBUP or XRNTX. Phase 1 will recruit 60 participants and Phase 2 will recruit 200 participants. The study length for each participant is comprised of up to 30 days of screening and baseline evaluations (called “week 1”), a 12-week open label trial (medication phase), and one follow-up visit 4 weeks after end of medication phase. The overall duration of the project will be 5 years (60 months). We intend to recruit 4 subjects per month for 40 months.

Table 1. Study timeline

Year/Phase	Year 1 (Phase 1)				Year 2 (Phase 1)				Year 3 (Phase 2)				Year 4 (Phase 2)				Year 5 (Phase 2)			
Quarter	Q1	Q2	Q3	Q4																
Preparation	X	X	X	X					X	X										
Recruitment		X	X	X	X	X	X	X	X	X	X	X	X	X	X	X	X			
Data Collection		X	X	X	X	X	X	X	X	X	X	X	X	X	X	X	X			
Data Analysis/QC			X	X	X	X	X	X	X	X	X	X	X	X	X	X	X	X	X	X
Publication				X	X			X	X			X	X			X	X	X	X	X

Figure 1: Outline of study interventions

3.2 Primary Study Endpoints (see Table in the Schedule of Activities (SoA), [Appendix Section 12.1](#)).

Clinical:

- 1) percent of the urine drug screen (UDS) tests positive for opioids during the last month of participation.
- 2) The number of study interventions (1,2 or 3) participant adhered to.

Surrogate: Brain fMRI response in three cognitive domains:

- 1) Response inhibition (Go-NoGo task)
- 2) Drug cue reactivity (Opioid Cues task)
- 3) Emotional identification (IDemo Task)
- 4)

Primary Hypothesis:

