4 STUDY PLAN

4.1 Study Design:

Single-blind, prospective study with Phase 1 (N = 60) to show feasibility and Phase 2 (N = 200) to confirm Phase 1 findings if they meet the milestones of effect size. This is to comply with the structure of the two-phase R61/R33 NIH funding mechanism. Both Phases will use the same sequence of data collection ([Section 3.1, Figure 2](#)).

Rationale for the study duration: Early medication effects are considered to be strong predictors of long term effectiveness both at the clinical (e.g. tolerability and symptom relief) and at the neural systems and pharmacodynamic levels (McDermott et al 2015). XRNTX exhibits high drop-out rate in the first 2 months of treatment, with 50% to 75% retention at the 3rd XRNTX injection (Wang et al 2015, Lee et al 2017). In a trial of sublingual buprenorphine, retention at 3 months was approximately 75% and relapse rates defined as repeated opioid positive urines were almost unchanged between 3 and 6 months time points (Lee et al 2017). Thus, a 70-day follow up period provided by two monthly XRNTX or XRBUP injections is a necessary and sufficient time window for a neurobiological evaluation of the mechanisms of relapse vulnerability while minimizing the effect of unrelated variables such as change in family, employment or medical status, on the outcome variable. We optimize the two-phase design by designing experiments that would generate data that could serve two purposes: the initial Phase 1 exploratory and milestone target and then part of the Phase 2 sample that would address confirmatory questions that require a sample size that neither phase could reach separately.

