9 STATISTICAL CONSIDERATIONS

9.1 Statistical Hypotheses

Overview of primary hypotheses: Our primary response will be a binary indicator of treatment failure on the XRNTX or XRBUP regimen, defined as ≥ 2 weekly UDS positive for opioids, or self-report of ≥ 2 periods of three or more days of opioid use, or refusing XRNTX or XRBUP, or dropping out of study entirely. In hypotheses H1a and H1b, we are examining the effects of small, pre-specified, sets of measures, so our analyses will focus on model fit and prediction, and not on model selection. In hypothesis H1c, we search for best sets of predictors among demographic and clinical-behavioral variables, and over sets of brain/neural measures, so our focus is on model selection and on avoiding overfitting to the available data.

R61 Phase:

Hypothesis H1 (fMRI): For each of the cue reactivity (H1a), response inhibition (H1b), and connectivity (H1c) brain measured, we have a small number of neural responses associated with one or two regions of interest. These variables are continuously distributed, so we will test Hypotheses 1a, 1b and 1c using a repeated measures analysis of variance (rm-anova). The models will include a within-subject factor for Session (PRE vs ON) and a between-subject factor Group (XRNTX vs XRBUP), and their interaction. To accommodate the anticipated non-normal distributions of the response, we will use a generalized estimating equation (GEE) approach, using robust standard errors, using a compound symmetry working correlation structure for the within-subject correlations between the PRE and ON fMRI scans (Diggle PJ et al 2002). We will perform the rm-anova separately for each ROI (mPFC and VS for H1a, IFC for H1b, and VS-rtIFG and VS-mPFC for H1c). The hypotheses will be addressed by the Session by Group interaction, and we will obtain estimates and standard errors of the PRE vs ON change within each of the two groups, along with the size, standard error and significance of the differences between these estimates.

Sample size considerations for sample: The sample size is adequate for application of the GEE methods to obtain robust standard error (Lipsitz et al 1994). For a test of the PRE vs ON effect, our sample yields 80% power for a one-sided test that the ON levels will be Cohen's $d=0.4$ lower than the PRE levels, consistent with a decrease of Cohen's $d=0.5$ observed in our preliminary data and a decrease of Cohen's $d=0.3$ in the Suboxone sample.

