Effects of neural response on relapse vulnerability: Our primary outcome combines adherence to treatment and frequency of illicit opioid use during treatment. The primary outcome is a binary indicator of treatment success: if a patient provides ≥ 2 weekly UDS positive for opioids, or self-report of \geq two or more periods of ≥ 3 days of opioid use, or refuses XRNTX or XRBUP, or drops out of treatment entirely, then they will be classified as a treatment failure; otherwise they will be classified as a treatment success. We will calculate the PRE-ON change in %-signal-change for each of the regions and neural responses described in the R61 phase. We will use logistic regression models to predict the log-odds of treatment success (Aitkin et al 2009). The predictors in the model will be a binary factor for Group (XRNTX vs. XRBUP), and the neural change scores. We anticipate that there will be some greater PRE to ON changes in the XRNTX group than in the XRBUP group, so there will be some confounding between the effects of change score and the effects of Group on the rates of positive UDS. Thus, we will include Group first in our model, so evaluating the Group effect separate from the change-score effects, and then include the change scores in a model including Group, so evaluating the additional effect of change-scores in addition to the existing effects of Group. To assess whether the effects of the change scores differ between the XRNTX and XRBUP groups, we will also test for interaction effects between Group and each of the change-scores, by adding the interaction terms to the model that includes the group and neural change score main effects. We will check the assumptions underlying the logistic regression models (e.g. linearity of covariates effects on log-odds, outliers, influential observations) using standardized residuals, influence diagnostics, and graphical displays.

Sample size considerations for the sample: Analyses of Session by Group effects on neural response: For a one-sided test that the PRE vs ON effect is larger in the XRNTX group than in the XRBUP group, our sample of 70 per group yields 81% power for an effect of $d=0.42$ or greater. This effect is similar to the effects observed in the preliminary data. On the basis of the preliminary data we anticipate Group by Session effects of approximately $d=0.38$ in the VS and $d=0.42$ in the mOFC.

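### The CACE measures compliance with items that also make up treatment failure; if applied to that outcome, a between-arm adherence difference would appear as a complier effect

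*Combined protocol and SAP*

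**What the plan says.** Section 9.4.1, under Missing Data and Nonadherence, cites two methods "to obtain estimates of the intervention effect in a population compliant with treatment", which it calls the CACE. Compliance is to be measured as follows: "We will use urine drug screens, record of clinic visits and receipt of injectable medications as measures of compliance with assigned medication regime". The section gives no threshold, no rule for combining the three measures, no outcome, no reference treatment for people who do not comply, and no identifying assumptions. The two methods are cited by number and cannot be matched to the alphabetical list in Section 12.

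Section 9.1 builds treatment failure from overlapping material. Failure is "defined as ≥ 2 weekly UDS positive for opioids, or self-report of ≥ 2 periods of three or more days of opioid use", and the definition is completed by the participant who "or refuses XRNTX or XRBUP, or drops out of treatment entirely, then they will be classified as a treatment failure". Section 3.2 lists two clinical primary endpoints that overlap as well: "percent of the urine drug screen (UDS) tests positive for opioids during the last month of participation" and "The number of study interventions (1,2 or 3) participant adhered to".

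On expected adherence, Section 4.1 says: "XRNTX exhibits high drop-out rate in the first 2 months of treatment, with 50% to 75% retention at the 3rd XRNTX injection". The same section gives about 75% retention at 3 months, from a trial of sublingual buprenorphine.

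**The concern.** A CACE is read as the effect of the drug in people who take it. It needs assignment to act on the outcome only through the treatment taken (the exclusion restriction). Under the Section 9.1 definition, someone who refuses the injection or drops out is scored as a failure whatever their opioid use. Assignment then also acts through the scoring rule: a drug that more people abandon produces more failures, even if those who stay on either drug do equally well. Dividing that arm difference by compliance rescales a difference in drop-out and presents it as efficacy among compliers. For the number-of-injections endpoint the problem is complete, because that outcome is itself a compliance measure.

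A second difficulty does not depend on the outcome. Both arms are active. People who would comply with XRNTX and people who would comply with XRBUP may be different, and each group is seen in one arm only. Randomisation alone does not identify a single complier effect; further assumptions are needed and none is stated.

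**Working it through.** The plan gives no figure for the CACE, so there is none to reproduce. The check sets the true difference between compliers to zero and asks what a complier estimate for treatment failure would report.

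**Inputs**
- XRNTX adherence, cN: 50% to 75% (Section 4.1); midpoint (50 + 75)/2 = 62.5%.
- XRBUP adherence, cB: 75% (Section 4.1; a proxy, since it comes from sublingual buprenorphine).
- Success among adherers, s, equal in both arms: not in the documents. Assumed 80%, range 60% to 100%.
- Success among people who refuse or drop out: 0, by the Section 9.1 definition.
- Estimator: the Wald ratio (arm difference in success divided by XRBUP adherence). This is an assumption.

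**Step 1: formula.** Success in an arm is c × s. The arm difference is s(cB − cN), so the complier estimate is s(cB − cN)/cB.

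**Step 2: numbers at s = 0.80**
- cN = 0.50: success 0.60 v 0.40; difference 0.20; 0.20/0.75 = 0.267.
- cN = 0.625: success 0.60 v 0.50; difference 0.10; 0.10/0.75 = 0.133.
- cN = 0.75: difference 0; estimate 0.

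Spurious complier effect in favour of XRBUP, in percentage points:

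| XRNTX adherence | s = 60% | s = 80% | s = 100% |
|---|---|---|---|
| 50% | 20 | 27 | 33 |
| 62.5% | 10 | 13 | 17 |
| 75% | 0 | 0 | 0 |

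**Step 3: is the overlap the cause?** If non-adherers succeed at the same rate as adherers, so that non-adherence no longer fixes the outcome, the estimate is 0 even at 50% v 75%. In an intermediate case, with non-adherers succeeding 20% of the time and adherers 80%, the estimate is (0.80 − 0.20) × (0.75 − 0.50)/0.75 = 0.20.

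**Step 4: how often would it look significant?** In 40,000 simulated trials per setting, with a two-sided 5% pooled z test on the arm difference (the numerator of the ratio):

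| XRNTX v XRBUP adherence | 70 per group, s = 60% to 80% | 80 per group, s = 60% to 80% |
|---|---|---|
| 50% v 75% | 45% to 67% | 50% to 71% |
| 62.5% v 75% | 14% to 22% | 15% to 24% |
| 75% v 75% | about 5% | about 5% |

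Sections 9.1 and 9.2 give 70 and 80 per group respectively, so both are shown. The arm difference in treatment failure is real in these trials; the error lies in attributing it to compliers.

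**Step 5: the other route.** Comparing observed adherers directly gives a mean difference of 0 in every setting above, as it should. But if compliant also requires clean urines, nearly all compliers are successes by construction, and a real difference in opioid use would be pushed toward zero. The direction of the distortion therefore depends on choices that Section 9.4.1 leaves open.

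**The case against.** A reader might infer that the planned analysis is bound to report a complier effect. The documents do not support that.

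- **The outcome is not named.** The paragraph opens with the longitudinal analyses and refers to the main hypotheses. The primary hypothesis is the fMRI Session by Group interaction, which contains no urines, visits or injections. Nothing commits the plan to a CACE on the composite. This stands, and makes the point conditional.
- **Adherence may be equal.** The XRNTX range of 50% to 75% reaches the buprenorphine figure, where the spurious effect is zero. The 75% is not from the injectable product, and the 25% dropout anticipated in Section 9.1 is not split by arm. This also stands.
- **The estimator is assumed.** The cited methods may not be a Wald ratio. A reader might divide by XRNTX adherence instead and obtain 0.20/0.50 = 40 points or 0.10/0.625 = 16 points; nothing in the documents justifies that divisor.
- **Not every non-complier is a failure.** One positive urine or a few missed visits could count as non-compliance without meeting the failure definition. This is correct. It weakens the overlap without removing it, as the 20-point intermediate result in Step 3 shows.
- **Urine screens might mean detecting the assigned drug.** The panel in Section 6.1 includes buprenorphine but does not list naltrexone, so as proof of dosing it would serve one arm only.
- **The analysis is minor.** No hypothesis, milestone or power calculation depends on it. That is fair, and it limits the weight of the point.

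**Conclusion.** The point holds conditionally. The stated compliance measures overlap with treatment failure and with both clinical primary endpoints. If the CACE is computed for treatment failure, the exclusion restriction fails and a between-arm adherence difference is reported as a complier effect: 20 to 33 points at 50% XRNTX retention, 10 to 17 at 62.5%, and none at 75%. These figures rest on a Wald-type estimate, 75% XRBUP retention taken from sublingual buprenorphine, an assumed 60% to 100% success among adherers, and failure of everyone who refuses or drops out. The component overlap does not reach the fMRI outcomes. The need for stated assumptions to define one complier effect across two active arms applies to every outcome.

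**What to change.** In Section 9.4.1, under Missing Data and Nonadherence:

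1. Define compliance by receipt of scheduled injections only, and delete urine screens and clinic visits from the definition. Section 2.2.1 already treats receipt of an injection as fully verifiable.
2. State that no CACE will be computed for the treatment-failure composite or the number-of-injections endpoint.
3. Name an outcome that does not count refusal or drop-out as failure, for example the fMRI change or the weekly opioid-use measures in Section 9.1. The weekly measures are partly urine-based, so they are suitable only once urines are out of the compliance definition.
4. Label any adherence-adjusted estimate as a sensitivity analysis and state its identifying assumptions, including the reference treatment and how compliers with two active drugs are made comparable.

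The cost is SAP wording, with no new data collection. One secondary sensitivity estimate is dropped or replaced.

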8.3.5 Adverse Event Reporting

Once per week, a medical sub-investigator must seek information on adverse events by specific questioning and, as appropriate, by examination. However, research staff should notify a medical sub-investigator any time an adverse event is reported by a subject. Information on all adverse events should be recorded immediately in the source document, and also in the appropriate adverse event module of the case report form (CRF). All clearly related signs, symptoms, and abnormal diagnostic procedures results should be recorded in the source document, though should be grouped under one diagnosis.

8.3.6 All adverse events occurring during the study period must be recorded. The clinical course of each event should be followed until resolution, stabilization, or until it has been determined that the study treatment or participation is not the cause. Serious adverse events that are still ongoing at the end of the study period must be followed up to determine the final outcome. Any serious adverse event that occurs after the study period and is considered to be possibly related to the study treatment or study participation should be recorded and reported immediately. Serious Adverse Event Reporting

Adverse event reporting to the FDA will follow the study IRB protocol. Briefly, a serious adverse event will be reported to the study sponsor ([name]) by email or telephone within 72 hours of when the event is reported to any of the study staff. A Serious Adverse Event (SAE) form must be completed by the investigator and faxed to the study sponsor within 72-hours. The investigator will keep a copy of this SAE form on file at the study site. Report serious adverse events by phone and facsimile to the study regulatory sponsor: [name]. (o) [contact], (f) [contact], [contact]

At the time of the initial report, the following information would be provided:

Study identifier	Whether study treatment was discontinued
Study Center	
Subject number	The reason why the event is classified as serious
A description of the event	Investigator assessment of the association between the event and study treatment
Date of onset	
Current status	

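### Safety is summarised on adverse-event totals and crude percentages with no stated exposure handling, so if retention differs the arm observed for less time could look safer

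*Combined protocol and SAP*

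**What the plan says.** The safety paragraph of section 9.4.1 names "Total number of adverse events, adverse events leading to discontinuation (in the judgment of the study physician", and the percentage "of patients reporting at least one adverse event", with laboratory values, vital signs and signs of clinical worsening. It adds one model: "medication group, gender, age and other clinical variables will be entered into a generalized linear mixed effects model to predict adverse events". The response (count, any event, or event in a given week), the link and any term for time observed are not given.

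I found no incidence rate, person-time denominator, offset or time-to-first-event analysis for adverse events in the documents. Sections 8.3.1 and 8.3.6 refer to the course of the study and the study period, but no start and end day is set for the analysis. Section 9.3 defines one all-treated population. The missing-data text in 9.4.1 concerns the longitudinal use outcomes and the main hypotheses, not adverse events.

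On ascertainment, section 8.3.5 says: "Once per week, a medical sub-investigator must seek information on adverse events by specific questioning". On retention, section 4.1 says: "XRNTX exhibits high drop-out rate in the first 2 months of treatment, with 50% to 75% retention at the 3rd XRNTX injection". It also says: "In a trial of sublingual buprenorphine, retention at 3 months was approximately 75" per cent.

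**The concern.** A count of events, or the chance of at least one, grows with the time a person is watched. Events here are elicited mainly at contacts, so a participant who stops attending largely stops contributing. If one arm loses participants earlier, equal underlying event rates give that arm fewer counted events and fewer people with any event. A person-level model of totals without an exposure term would carry the same difference.

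Section 4.1 leaves room for such an imbalance. Section 7.2 also allows an investigator to withdraw a participant whose injection is more than 14 days overdue, so missed treatment can become missed observation. What is at stake is the tolerability comparison between the two drugs.

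**Working it through.** The plan states no event rate, power or sample size for safety, so there is no safety figure to reproduce.

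**Inputs from the documents**
- Schedule of Activities: Injection 1 on day 10, Injection 3 on day 70, end of study on day 100. A completer is observed for 90 days from Injection 1.
- Section 4.1: XRNTX retention 50% to 75% at the third injection; about 75% at 3 months for sublingual buprenorphine, used here as a stand-in for XRBUP.
- Section 9.2: 80 per group, for illustration (section 9.1 has 70; the ratios do not depend on it).

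**Assumptions not in the documents**
- Equal, constant event rates in both arms.
- Everyone who stops treatment also leaves observation.
- In the base case, drop-out is spread evenly over days 10 to 70, a mean of 30 days after Injection 1.

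**Mean observed days** = r × 90 + (1 − r) × (mean days to drop-out), where r is retention.
- r = 0.50: 45 + 15 = 60
- r = 0.625: 56.25 + 11.25 = 67.5
- r = 0.75: 67.5 + 7.5 = 75

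With equal rates, the ratio of expected totals is the ratio of mean days, XRNTX over XRBUP:

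| Scenario | Days | Ratio |
|---|---|---|
| 50% v 75%, drop-out spread | 60 v 75 | 0.80 |
| 50% v 75%, all leave at day 70 | 75 v 82.5 | 0.91 |
| 50% v 75%, all leave just after Injection 1 | 45 v 67.5 | 0.67 |
| 62.5% v 75%, drop-out spread | 67.5 v 75 | 0.90 |
| 75% v 75% | 75 v 75 | 1.00 |
| Those who stop stay in follow-up | 90 v 90 | 1.00 |

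Counting the base case from day 0 adds 10 days to each arm: 70 v 85, ratio 0.82, or about 18% lower.

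**Percentage with at least one event.** Take a rate at which half of completers have an event, ln 2 / 90 per day. Over 60 days the rate totals 0.462. The probability for those who leave is 1 − (1 − e^−0.462)/0.462 = 0.199.
- XRNTX: 0.5 × 0.5 + 0.5 × 0.199 = 35.0%
- XRBUP: 0.75 × 0.5 + 0.25 × 0.199 = 42.5%

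**Could this be mistaken for a finding?** At an assumed 1 event per 30 days and 80 per arm, the base case gives 80 × 60/30 = 160 v 80 × 75/30 = 200 events. As Poisson counts, z = (200 − 160)/√360 = 2.11. XRNTX would then appear nominally lower (two-sided 0.05) about 56% of the time, against about 2.5% with equal exposure. At 0.25 and 0.5 events per 30 days the chances are 18% and 32%.

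**What an offset does.** Dividing by observed time returns an expected rate ratio of 1.00 in every scenario above, because the rate is constant. If instead all events fell in induction (days 0 to 10), before anyone left, totals would be equal. Rates per person-day from day 0 would then differ by 85/70 = 1.21, against XRNTX. A single person-time rate is therefore not a neutral correction when events cluster early.

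**The case against.** A reader might infer that XRNTX will look safer. The documents do not support that. The XRNTX range reaches 75%, the same as the comparator figure, and that figure is for a sublingual product. Section 2 says the long-acting formulations remove an imbalance between monthly naltrexone and daily sublingual buprenorphine, which cautions against carrying the figure across. The drop-out anticipated in section 9.1 is 25%, not split by arm.

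Leaving treatment is also not the same as leaving observation. Section 4.4 offers continued visits, section 3.4 encourages them and adds twice-weekly remote monitoring, and section 2.3.2 expects staff to keep contact after pharmacotherapy ends. The calculation assumes no take-up. This objection stands, and it makes the 20% conditional. But take-up is not assured, and no XRBUP figure exists to show that retention will match.

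The mixed model may already handle exposure. With a weekly response, absent weeks simply do not enter. The text says the safety model parallels the analysis of therapeutic response, but section 9.1 has both a person-level failure indicator and weekly binary measures, so the parallel does not settle the unit. The supportable point is that exposure handling is unspecified, not that the model is shown to be biased.

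Direction also varies by measure. Events leading to discontinuation may be more frequent in the arm with more exits, and early induction or injection-site events are little affected by later exit.

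Finally, the primary aim is an fMRI interaction, and no powered safety hypothesis rests on this paragraph. That limits the weight of the point but does not remove it.

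**Conclusion.** The concern holds in conditional form. Two of the named measures depend on observation time, and no exposure adjustment is specified. If retention is 50% v 75%, event rates are equal and constant, and those who stop also leave follow-up, raw totals would be about 20% lower on XRNTX from Injection 1. The range is about 9% to 33% by drop-out timing, and the figure is about 18% if counted from day 0. At 62.5% v 75% retention it is 10%. It is nil at equal retention or with full continued follow-up.

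The 20% pairs the low end of the XRNTX range with a sublingual-buprenorphine figure, so it illustrates what the plan's figures permit and is not a forecast.

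**What to change.** In the safety paragraph of section 9.4.1:

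1. Define the adverse-event observation window, with one stated start point and a stated end, and say whether time after stopping study drug counts.
2. State the model's response unit. Either model weekly event occurrence over observed weeks with study week in the model, or model counts with log observed person-time as an offset (negative binomial, or Poisson with robust standard errors).
3. Report exposure-adjusted rates and time to first event by arm, alongside the raw totals and percentages.
4. Because a person-time rate assumes a roughly constant hazard, also report rates by period: induction, and after Injection 1.

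The cost is SAP wording and a little more analysis. Section 9.4.1 already plans to use records of clinic visits and injections received, which can supply much of the observed time.
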